1.3.2 Randomization and Blinding

1.3.2.1 Randomization

The subjects, who are enrolled after successful screening and informed consent, will be randomized at a 3:1 ratio using the block randomization with a stratification factor of the site to receive the test drug SYN023 or control drug HRIG according to the same injection procedure, followed by a vaccination of rabies vaccine.

In the study, subjects are randomized using the Interactive Web Response System. The blinded randomization code is generated by the independent unblinded randomization statistician of the statistical facility with the subject randomization list and the study drug randomization list (blinded randomization code) using SAS software (Version 9.4) according to the protocol. The subject randomization list includes the site number, the subject randomization number (i.e., study number), and the group of study drug (collective name for the test drug SYN023 and the control drug HRIG) corresponding to the subject randomization number. The drug randomization list includes the drug randomization number and the study drug corresponding to the drug randomization number. The subject randomization list and drug randomization list (blinded randomization code) are uploaded by the unblinded database designer to the Interactive Web Response System (IWRS) to

complete the automatic matching between the IWRS and EDC. After completion of the system setup, the investigator or his/her designee will add a subject in the EDC, and assign a randomization number in the IWRS according to the subject's site after confirming his/her eligibility. Then a drug number for use at each dosing visit will be automatically assigned according to the study drug group to which the subject is randomized, and relevant study staff on the study site will administer the subject according to the drug number assigned by the system. The entire randomization is completed in the EDC and IWRS system, where user authorization is strictly controlled to ensure the maintenance of blindness during the study. The randomization number of any randomly assigned subject, who withdraws/is withdrawn from the clinical trial for any reason, will not be reassigned to other subjects regardless of the administration of study drug.

1.3.2.2 Drug Blinding

In order to reduce/avoid procedural bias, a double-blind design is adopted, where drug assignment is blinded to the randomization statistician and other blinding personnel, and the study drugs are uniformly packaged and sealed with the same boxes so that the test drug and control drug are identical in appearance. This prevents the staff with access only to the packaging of the product from getting aware of the type of drugs received by the subject, thereby ensuring the blindness of the used study drug. Injection giver and pharmacist are unblinded in the study. Any study-related personnel, except unblinded injection giver, are not allowed to unseal and access the study drug, to ensure that the subject is blinded to the size of study drug package. The syringes are also appropriately shielded to ensure that the subject is blinded to the color and dose of study drug. In this way, the subject is kept blinded to the study drug as he/she cannot find which study drug was administered with the available information.

The randomization statistician and other staff who are not involved in conduct of the clinical trial are responsible for preparation of the blinded randomization codes of study drug at the site. Under the guidance of the randomization statistician, relevant staff will stick the printed label of randomization numbers on the corresponding container and outer package of the test/control drug according to the blinded randomization code, and seal the packages properly with sealing labels.

After preparing the blinded randomization code, the blinded randomization code should be sealed and archived by the randomization statistician. Relevant records must be kept for generating the blinded randomization code throughout the process. The staff involved in generation of the blinded randomization code shall not participate in other work relating to this clinical trial, and shall not disclose the blinded randomization code to any staff involved in conduct of the clinical trial.

1.3.2.3 Maintenance of Blinding

Due to the different doses of the test drug and the control drug (0.1 mL/kg of the test drug and 0.2 mL/kg of the control drug), blinding should be maintained for the subjects, the investigator, and the laboratory test staff throughout the study.

- 1) During the study, subjects, blinded investigator and project members involved in any evaluation of endpoints, data review and data analysis in the study shall be blinded to the study grouping.
- 2) After the drug is packaged and assigned with a blinded code, each box should be sealed with a sealing label and should not be opened at will. Before vaccination, the injection giver should check the sealing label for intactness. If any vaccine is found to have broken sealing label when handing over to the injection giver by the pharmacist, it should be disposed as damaged vaccine.
- 3) After the pre-injection procedures are completed, the medical guide will lead the subjects into the vaccination room one by one to ensure that only one subject is receiving drug injection in the vaccination room at one time.
- 4) During drug dispensing and vaccination, necessary action should be taken to ensure that the subjects cannot see any identification information of the drug to be administered (such as shape of the outer package and syringe, and color of the drug);
- 5) Designated staff should be assigned to give the injection and manage the study drug only, without participating in any other tasks of the study, and should sign a non-disclosure agreement, stating their non-disclose of any information that may cause leakage of the blinded code to any other staff (including investigators involved in clinical study evaluation, subjects, serum sample analysts, blinded CRAs and QC staff, data managers, etc.);
- 6) The injection giver should return the empty vials/boxes of the used drugs into the original packaging boxes, and timely make a reconciliation and transfer to the pharmacist for storage after completion of the work on the same day. After the site is closed out and the authorization from sponsor is obtained, the study site should uniformly transfer the empty vials/boxes to the medical waste disposal company or the sponsor for destruction and the destruction records should be retained.
- 7) The monitoring and quality control for drug management and injection should be completed by unblinded CRAs and QC staff.

1.3.3 Sample Size

Primary study hypothesis:

The test group is superior to the control group in the geometric mean concentration of RVNA on Day 8 post-dose (the lower limit of the 95% confidence interval (CI) of the geometric mean concentration of RVNA (test group/control group) > 1.2)

Based on the study hypothesis, the lower limit of the 95% confidence interval (CI) of the geometric mean concentration of RVNA (test group/control group) is > 1.2 , a final sample size of 16 subjects (12 subjects in the test group and 4 subjects in the control group) is required with a type I error of 0.025 (one-sided), a power of

90%, an estimated geometric mean concentration of RVNA (test group/control group) on Day 8 post-dose of 11.9, and a coefficient of variation (CV) of 120.5%, when assigning the subjects to the test group/control group at a ratio of 3:1 and considering a dropout rate of 20%. The current 1000 subjects are sufficient to ensure a 100% power under the same hypothesis.

Secondary study hypothesis:

- 1) The test group is superior to the control group in the geometric mean concentration of RVNA on Day 4 post-dose (the lower limit of the 95% confidence interval (CI) of the geometric mean concentration of RVNA (test group/control group) > 1.2)

Based on the study hypothesis, the lower limit of the 95% confidence interval (CI) of the geometric mean concentration of RVNA (test group/control group) is > 1.2 , a final sample size of 12 subjects (9 subjects in the test group and 3 subjects in the control group) is required with a type I error of 0.025 (one-sided), a power of 90%, an estimated geometric mean concentration of RVNA (test group/control group) on Day 4 post-dose of 13.75, and a CV of 63.25%, when assigning the subjects to the test group/control group at a ratio of 3:1 and considering a dropout rate of 20%. The current 1000 subjects are sufficient to ensure a 100% power under the same hypothesis.

- 2) The test group is non-inferior to the control group in the geometric mean concentration of RVNA on Day 99 post-dose (the lower limit of the 95% confidence interval (CI) of the geometric mean concentration of RVNA (test group/control group) > 0.8)

Based on the study hypothesis, the lower limit of the 95% confidence interval (CI) of the geometric mean concentration of RVNA (test group/control group) is > 0.8 , a final sample size of 308 subjects (231 subjects in the test group and 77 subjects in the control group) is required with a type I error of 0.025 (one-sided), a power of 90%, an estimated geometric mean concentration of RVNA (test group/control group) on Day 99 post-dose of 86.94, and a CV of 17.32%, when assigning the subjects to the test group/control group at a ratio of 3:1 and considering a dropout rate of 20%. The current 1000 subjects are sufficient to ensure a 100% power under the same hypothesis.

- 3) The test group is non-inferior to the control group in the antibody positive rate of RVNA ($RVNA \geq 0.5$ IU/mL) on Day 99 post-dose (the lower limit of 95% CI of RVNA positive rate (test group/control group) > 0.9)

Based on the study hypothesis, the lower limit of the 95% CI of the ratio of antibody positive rates (test group/control group) is > 0.9 , a final sample size of 52 subjects (39 subjects in the test group and 13 subjects in the control group) is required with a type I error of 0.025 (one-sided), a power of 90%, an estimated ratio of antibody positive rates (test group/control group) on Day 99 post-dose of 1, and a CV of 98.7%, when assigning the subjects to the test group/control group at a

ratio of 3:1 and considering a dropout rate of 20%. The current 1000 subjects are sufficient to ensure a 100% power under the same hypothesis.

4) The SYN023 plus Rabies Vaccine group is superior to the HRIG plus Rabies Vaccine group in AUEC₁₋₁₅ of RVNA GMC (the lower limit of 95% CI of AUEC₁₋₁₅ ratio of RVNA GMC (test group/control group)>1.1)

Based on the study hypothesis, the lower limit of the 95% CI of AUEC₁₋₁₅ ratio of RVNA GMC (test group/control group) is > 1.1, a final sample size of 900 subjects (675 subjects in the test group and 225 subjects in the control group) is required with a type I error of 0.025 (one-sided), a power of 90%, an estimated AUEC₁₋₁₅ ratio of RVNA GMC (test group/control group) post-dose of 147.55%, and a CV of 142%, when assigning the subjects to the test group/control group at a ratio of 3:1 and considering a dropout rate of 20%. The current 1000 subjects are sufficient to ensure a 96.9% power under the same hypothesis.

2 General Statistical Considerations

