--	--

	
group/control group) should be > 0.9.
 
Based on this hypothesis, i.e., the lower limit of the 95% confidence interval of the geometric mean concentration of RVNA (experimental group/control group) should be > 0.8, it is assumed that the type I error is 0.025 (one-sided) and the Power is 90%; the estimated antibody protection level ratio (experimental group/control group) should be 1 on Study Day 15 after administration and the estimated protection level of the control group is 98.7%; and the randomization of the experimental group/control group is 3:1. Therefore, 52 cases are needed, including 39 cases in the experimental group and 13 cases in the control group, given a drop-out rate of 20%. The existing 1,000 cases will ensure a Power of 100% when the hypotheses remain unchanged.
 
4)The area under the efficacy curve for the GMC of RVNA from Study Day 1 to Day 15 (AUEC₁₋₁₅) for the "SYN023 + rabies vaccine" group should be superior to that of the "HRIG + rabies vaccine" group (the lower limit of the 95% confidence interval of the AUEC₁₋₁₅ (experimental group/control group) for the GMC of RVNA from Study Day 1 to Day 15 should be > 1.1);
 
Based on this hypothesis, i.e., the lower limit of the 95% CI of the AUEC₁₋₁₅ (experimental group/control group) for the GMC of RVNA from Study Day 1 to Day 15 should be > 1.1, it is assumed that Type I error is 0.025 (one-sided) and the test Power is 90%; the estimated value of AUEC₀₋₁₄ (experimental group/control group) for the GMC of RVNA from Study Day 1 to Day 15 is 147.55%, and CV% is 142%; and the randomization of the experimental group/control group is 3:1. Therefore, 900 cases are needed, including 675 cases in the experimental group and 225 cases in the control group, given a drop-out rate of 20%. The existing 1,000 cases will ensure a Power of 96.9%.

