Based on this hypothesis, i.e., the lower end of the 95% confidence interval for antibody protection level ratio (experimental group/control group) > 0.8 , assuming that type I error is 0.025 (one-sided), study power is 90%, estimated antibody protection level ratio (experimental group/control group) on Study Day 15 of administration is 1, estimated protection level of control group is 98.7%, distribution ratio of samples is 3:1 (experimental group/control group), and sample exclusion rate is 20%, 52 samples will be required (39 samples for experimental group and 13 samples for control group). The existing 1,000 cases will ensure a test power of 100% when the hypotheses remain unchanged.

- 3) AUEC₁₋₁₅ of RVNA GMC of SYN023+rabies vaccine is superior to that of HRIG+rabies vaccine (the lower end of the 95% confidence interval for RVNA GMC

$AUEC_{1-15}$ (experimental group/control group) > 1.1 .

Based on this hypothesis, i.e., the lower limit of the 95% confidence interval of the $AUEC_{1-15}$ (experimental group/control group) for the GMC of RVNA from Study Day 1 to Day 15 should be >1.1 , it is assumed that Type I error is 0.025 (one-sided) and the test power is 90%; the estimated value of $AUEC_{1-15}$ (experimental group/control group) for the GMC of RVNA from Study Day 1 to Day 15 is 147.55%, and CV% is 142%; and the randomization of the experimental group/control group is 3:1. Therefore, 900 cases are needed, including 675 cases in the experimental group and 225 cases in the control group, given a drop-out rate of 20%. The existing 1,000 cases will ensure a test power of 96.9% when the hypotheses remain unchanged.

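### The 52 subjects that SAP 1.3.3 gives for the Day 99 positive-rate test are the number for a ratio limit of 0.8, not the stated 0.9, and its 98.7% CV is a control-group rate

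*SAP*

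**What the plan says.** **SAP 1.3.3, secondary hypothesis 3 (Day 99).** The criterion is "the lower limit of the 95% CI of the ratio of antibody positive rates (test group/control group) is > 0.9". The size is given as "test group/control group) is > 0.9 , a final sample size of 52 subjects (39 subjects in the test group", with 13 controls. It "is required with a type I error of 0.025 (one-sided), a power of 90%, an estimated ratio of antibody positive rates", with 3:1 allocation and 20% dropout. The remaining inputs are a true ratio and a CV: "on Day 99 post-dose of 1, and a CV of 98.7" per cent.

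**Protocol 13.3, secondary hypothesis 2 (Day 15).** The limit is 0.8: "confidence interval for antibody protection level ratio (experimental group/control group) > 0.8". The error rate, power, true ratio, allocation and loss are the same, and so is the result, 52 (39/13). Here the last input is a proportion: "estimated protection level of control group is 98.7" per cent.

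**Protocol synopsis.** The hypotheses section puts this test on Day 15 with a limit of 0.8. In the sample size section the heading for the same Day 15 test ends "group/control group) should be > 0.9". The calculation below it uses 0.8 (worded there as a limit on the GMC ratio) and again gives 52.

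**Day.** The protocol's own secondary objectives (synopsis and section 2.2) put non-inferiority of this rate on Day 99, as the SAP does.

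**Declared changes.** SAP section 5 lists only the added Wald and CMH analyses as departures from the protocol.

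**The concern.** With every other stated input equal, a tighter non-inferiority limit needs more subjects. The SAP's limit of 0.9 and protocol 13.3's limit of 0.8 cannot both lead to 52 (39/13) by one method. A CV also has no place in a sample size for a ratio of two proportions. The input needed is a control rate, and the SAP gives none for Day 99.

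The test is confirmatory. Under SAP 2.4 it is run at one-sided 0.025, and it must succeed before AUEC from Day 1 to Day 15 can be tested confirmatorily. A stated requirement for such a test should be reproducible from its stated inputs.

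**Working it through.** **Inputs.** One-sided type I error 0.025 (z = 1.960), power 90% (z = 1.2816), true ratio 1, 3:1 allocation and 20% loss, all from SAP 1.3.3 and protocol 13.3. The control rate p = 0.987 comes from protocol 13.3, where it is a Day 15 figure. Using it for Day 99 is an assumption.

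**Formula (Farrington-Manning, ratio of proportions).** Let R be the limit, k = 3, and n the evaluable controls, with 3n in the test group.

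- d = p(1 − R)
- V1 = p(1 − p)(1/k + R²)
- V0 = a(1 − a)/k + R²·b(1 − b), where a = R·b are the maximum-likelihood test and control rates when the true ratio equals R
- n = [(1.960·√V0 + 1.2816·√V1)/d]²

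**Step 1: reproduce 52 at R = 0.8.**
- a = 0.7973, b = 0.9966, V0 = 0.05606, V1 = 0.01249, d = 0.1974
- n = [(0.4640 + 0.1432)/0.1974]² = 9.46, so 10 controls and 30 test, 40 evaluable (power 92%)
- Loss: 10/0.8 = 12.5, rounded up to 13 controls; 3 × 13 = 39 test; total 52

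Both the total and the split match the documents.

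**Step 2: same method at R = 0.9.**
- a = 0.8968, b = 0.9964, V0 = 0.03376, V1 = 0.01467, d = 0.0987
- n = [(0.3601 + 0.1552)/0.0987]² = 27.26, so 28 controls and 84 test, 112 evaluable
- Loss: 28/0.8 = 35 controls; 3 × 35 = 105 test; total 140

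**Step 3: power of 52 less 20% (10 + 30) at R = 0.9.**
Φ[(0.0987·√10 − 0.3601)/√0.01467] = Φ[(0.3121 − 0.3601)/0.1211] = Φ(−0.396) = 35%.

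**Step 4: unpooled Wald as a cross-check.** n = (1.960 + 1.2816)²·V1/d².
- R = 0.9: 15.8, so 16 + 48 = 64 evaluable and 20 + 60 = 80 enrolled. Power at 10 + 30 is Φ(0.3121/0.1211 − 1.960) = Φ(0.617) = 73%.
- R = 0.8: 3.4, so 4 + 12 = 16 evaluable and 5 + 15 = 20 enrolled. Wald therefore did not produce the documents' 52.

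**Step 5: sensitivity to the Day 99 control rate** (Farrington-Manning, R = 0.9, after 20% loss; the rates are assumptions).

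| Assumed control rate | Total enrolled |
|---|---|
| 95% | 300 |
| 97% | 212 |
| 98.7% | 140 |
| 99.5% | 100 |

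**Step 6: 98.7% read literally as a CV.** A log-scale calculation for means gives about 960 subjects at 0.8 and about 4,296 at 0.9. The 52 was not derived from a CV.

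**Step 7: the planned trial.** 1,000 less 20% leaves 600 + 200. At R = 0.9 and p = 0.987 power is about 100%, and likewise at 0.8. At an assumed rate of 95% and R = 0.9, V0 = 0.04898 and V1 = 0.05431, so power is Φ[(0.095·√200 − 1.960·√0.04898)/√0.05431] = Φ(3.90), above 99.9%.

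**The case against.** **The number drives nothing.** The AUEC hypothesis needs 900 and 1,000 are planned. The SAP's claim of 100% power with 1,000 is correct at either limit. This stands. A reader might infer that the Day 99 test is underpowered; Step 7 shows that it is not.

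**The SAP did not create the mismatch.** A reader might infer that the SAP moved the day and tightened the limit without recalculating. The documents do not support that as a simple account. The protocol synopsis already joins a 0.9 heading to a 0.8 calculation and to 52, and Day 99 is already the day in the protocol's objectives. The conflict begins inside the protocol and the SAP inherits it. This stands.

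**140 is not simply the right answer.** It presumes that 0.9 is the limit to keep, that Farrington-Manning is the method and that 98.7% holds at Day 99. Neither document names a method or gives a Day 99 control rate. If the limit is settled at 0.8 and the rate at 98.7%, 52 is correct and the stated limit is what must change. This also stands, so 140 can only be conditional.

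**Some method might give 52 at 0.9.** One comes close. An uncorrected log-ratio Wald test, enumerated exactly, reaches 91% power at 40 evaluable. However, its power falls back to between 86% and 90% from 44 to 60 evaluable, its type I error at 10 + 30 is about 12% rather than 2.5%, and at 0.8 the same approach gives 28, not 52. It does not rescue the figure.

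**Conclusion.** The point holds as an error in the stated justification. The 52 (39/13) in SAP 1.3.3 is the Farrington-Manning size for a limit of 0.8 with a 98.7% control rate. It does not give 90% power at the 0.9 that the SAP states. If 98.7% is assumed for Day 99, the method that reproduces 52 requires 140 at 0.9, and 52 enrolled would give about 35% power. Unpooled Wald is milder (80 required, 73% power) but does not reproduce the documents' own figure. The requirement depends strongly on the unstated Day 99 rate, from 100 at 99.5% to 300 at 95%. The CV label is a plain error, since protocol 13.3 identifies the same 98.7% as a control-group protection level.

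The planned enrolment and the power of about 100% are unaffected. The importance is low.

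**What to change.** 1. Reconcile the limit (0.8 or 0.9) and the day (15 or 99) for this hypothesis across the protocol synopsis, protocol sections 2.2, 13.1 and 13.3, and SAP 1.3.3 and 2.4. Record the outcome in SAP section 5. The limit is a success criterion, so settle it before the Day 99 unblinding.
2. In SAP 1.3.3, replace the 98.7% CV with an assumed control-group positive rate for the day kept, and say where it comes from.
3. Name the sample size method.
4. Restate the required size for the limit kept. Under Farrington-Manning with a rate of 98.7%, that is 140 (105/35) at 0.9 or 52 (39/13) at 0.8. With another rate, recalculate.

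The cost is text in the two documents. If 0.9 is kept at 98.7%, the stated requirement rises from 52 to 140, but neither the enrolment of 1,000 nor the statement of 100% power changes.

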2.1 General Principles

The data analysis will be performed using SAS version 9.4 or above. Two-sided tests will be performed for all statistical analysis with an $\alpha = 0.05$ and two-sided confidence interval of 95%. In addition, continuous variables will be described using the number of subjects, mean, standard deviation, median, 25th percentile (Q1), 75th percentile (Q3), maximum, and minimum; and categorical variables will be described using the number and percentage of subjects. Table 1 shows the decimal places of statistical parameters.

Table 1. Decimal Places of Statistical Parameters

Statistics	Decimal Places
Mean, median, Q1, Q3	One more decimal place than the raw data, but no more than 3 decimal places.
Standard deviation, 95% CI	Two more decimal place than the raw data, but no more than 3 decimal places.
Max, Min	The same decimal places as the raw data, but no more than 3 decimal places.
Percentage	One decimal place; expressed as "100" if the percentage reaches 100% and "0" if the percentage is 0.
P value	Three decimal places; expressed as "< 0.001" and if P-value is less than 0.001. Expressed as ">0.999" and if P-value is greater than 0.999.

2.2 Definitions of Analysis Sets

Safety Set (SS): includes all randomized subjects who have received at least 1 dose of study drug, used as the Safety Set of the study. Based on the SS, the subjects will be analyzed for safety by actual treatment groups; and be analyzed for demographic, baseline, and efficacy endpoints by planned groups.

Per-Protocol Set (PPS): includes all randomized subjects who have received correct study drug, have been confirmed for eligibility to inclusion/exclusion criteria*, have completed the rabies vaccination on Study Day 29 as required by the protocol, have no major protocol violations affecting the efficacy evaluation, and have received sufficient wound treatment at all exposed sites and received study drug injections.

* Inclusion/exclusion criteria to be confirmed include: Category III rabies exposure with a duration of <24 hours; RVNA <0.1 IU/mL in serum collected from blood sampling at time “0” on study day 1 (WHO, 2013). In our previous clinical study experience, about 2% to 5% of enrolled subjects may have the history of vaccination with rabies vaccine. Their RVNA response may be much quicker and higher than the naive patients. Since the RVNA is a critical efficacy endpoint, the subjects with a RVNA \geq 0.1 IU mL, which indicated the prior use of rabies vaccine, should be analyzed separately.

In addition, subjects with (not limited to) the following conditions will likely be excluded from the PPS, depending on the discussion at the blinded data review meeting prior to database lock:

- Subjects will be excluded for the conditions that may impair the protection (such as immunodeficiency) as discovered after randomization.
- Subjects will be excluded if excessive treatment delay (>24 hours) is discovered.
- Subjects will be excluded if they will receive or have received protocol prohibited treatments.
- Subjects will be excluded if all of the bite wounds are discovered to have not been properly treated or injected.

The primary analysis of the efficacy endpoints will be performed by the randomized groups of study drugs based on the PPS.

